4.2.4 At the Two Month Reassessment Visit

- Frequency of exercise use (0 = not at all, or number of times per week)
- Effectiveness of the corrective exercise in correcting pain (0 = not at all, 1 = sometimes, 2 = most of the time, 3 = always)
- Side effects of the corrective exercise
- Satisfaction with use of the pelvic support belt (0 = not at all, 1 = mildly satisfied, 2 = moderately satisfied, 3 = very satisfied)

- Was the pelvic support belt worn during the day? (0 = not at all, 1 = sometimes, 2 = most of the time, 3 = always)
- Was the pelvic support belt worn at night? (0 = not at all, 1 = sometimes, 2 = most of the time, 3 = always)
- Side effects of the pelvic support belt
- Perceived need for further treatment 0 = not at all, 1 = possibly, 2 = probably, 3 = certainly)

5.0 Statistics

5.1 Outcome Measures

5.1.1A Primary Outcomes For the First Study

- difference in the change in ODI score in the initial treatment visit questionnaire and at the assessment visit one month later in the control group compared to the change from the treatment visit questionnaire to the 1 month assessment follow-up visit in the immediate SIFFT and exercise treatment group.
- difference in the change in ODI score in the treatment visit questionnaire and at the assessment visit, one month later, in the control group compared to the change from the treatment visit questionnaire to the 1 month assessment follow-up visit in the immediate pelvic support belt treatment group.

5.1.2A Secondary Outcomes For the First Study

- difference in the change in BPI NRS pain severity scores in the treatment visit questionnaire and at the assessment visit, one month later, in the control group compared to the change from the treatment visit questionnaire to the 1 month follow-up assessment visit in the immediate SIFFT and exercise treatment group.
- difference in the change in BPI NRS pain severity scores in the treatment visit questionnaire and at the assessment visit, one month later, in the control group compared to the change from the treatment visit questionnaire to the 1 month follow-up assessment visit in the immediate pelvic support belt treatment group.

5.1.1B Primary Outcome For the Follow-up Study

- difference in the change in ODI score in the assessment visit questionnaire and at the reassessment visit, two months later, for all groups.

5.1.2B Secondary Outcome For the Follow-up Study

- difference in the change in BPI NRS pain severity scores in the assessment visit questionnaire and at the reassessment visit, two months later, for all groups.

5.1.3 Other Measurements

- Change in pain level, immediately before and after the corrective exercises at
 - the treatment visit for members of group 1
 - the one-month follow-up assessment visit.
 - the two month reassessment visit
- Change in average pain level between the
 - treatment visit
 - and the one-month follow-up visit.
- Number of times the exercise was used per week
- Perceived effectiveness of the exercise
 - when first used with the physician
 - one month later,
 - and two months later for group 1
- How often the pelvic support belt was used during the day at the one month follow-up assessment visit for group 2.
- How often the pelvic support belt was used during the day at the 2 month reassessment visit for all participants.
- How often the pelvic support belt was used during the night at the follow-up assessment visit for group 2.
- How often the pelvic support belt was used during the night at 2 month reassessment visit for all participants.
- Perceived effectiveness of the pelvic support belt when first used and after one month of use for all participants.
- perceived effectiveness of the pelvic support belt when first used and after two months of use for group 2.

5.2 Statistical Analysis

Data will be analyzed using PASW Statistics 18, Release 18.0.0, IBM. Analysis will be performed by intention-to-treat. Descriptive statistics (mean value \pm standard deviation (SD)) will be calculated for outcome variables at each time point. Baseline between-group data will be analyzed for significant differences by t-tests for nominal variables and Pearson chi square tests for categorical variables. Baseline characteristics will be included in the model as covariates for those variables with a significant between group difference. Analyses of covariates will be applied to compare the groups for magnitude of change in the 0-10 NRS pain score and Oswestry Disability Index between baseline and each follow-up time point (0, 1 and 2 months). A two-tailed P value $<.05$ will be used as the statistical significance level.

- a Pearson's chi-square-test will be done to assess the significance of the difference in Oswestry low back disability score over a 1 month period between

those who are treated with the immediate SIFFT and exercise treatment group, the immediate pelvic support belt group and those who are in the observation group.

- A second Pearson's chi-square will be done to assess the significance of the difference in BPI NRS pain severity score over a 1 month period between those who are treated with the immediate SIFFT and exercise treatment group, the immediate pelvic support belt group and those who are in the observation group.
- A student t-test will be done to assess the significance of the difference in ODI score over a one month period when both treatments are used simultaneously.
- A student t-test will be done to assess the significance of the difference in BPI NRS pain severity score over a one month period when both treatments are used simultaneously.
- The average and standard deviation for all the other data will be calculated and reported on.

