4.2 Data Collected on All Participants with Nonaligned PSISs

4.2.1 At all visits

- Date of questionnaire (randomization and first treatment visit, one month assessment visit and two month reassessment visit)
 - Use of medications, cannabis, alcohol.
 - Use of other treatments: acupuncture, yoga, core exercises, chiropractic manipulation, massage, physiotherapy and other treatments.
 - The (ODI) questionnaire (appendix 2)
 - the BPI NRS Pain Severity Scale (appendix 1): On a scale of 0 (no pain) to 10 (worst imaginable pain) pain in the last 24 hours compared to previous recorded pain level (the participant will have this information available)
 - on average
 - at its worst
 - at its best
 - right now

the average of these values as well as the pain "right now" will be recorded.

4.2.2 At the Treatment visit and the One Month Follow-Up Visit:

- On which side the painful sacroiliac sprain is located and whether it is anteriorly or posteriorly rotated.
- Distance in centimetres between the lowest and the highest PSIS: before and, for group 1 participants, after the corrective exercise.
- Pain score 0 (no pain) to 10 (worst imaginable pain) following the exercise, for group 1 participants.
- Impression of pelvic support belt for group 2 participants

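### Baseline ODI and BPI are not fixed as covariates; the only written rule is a baseline significance screen, which would usually leave them out and cost precision

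*Combined protocol and SAP*

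**What the plan says.** Section 5.2 first tests the groups against each other at baseline: "Baseline between-group data will be analyzed for significant differences by t-tests for nominal variables and Pearson chi square tests for categorical variables". The result decides what is adjusted for: "Baseline characteristics will be included in the model as covariates for those variables with a significant between group difference". The next sentence is "Analyses of covariates will be applied to compare the groups for magnitude of change" in pain score and ODI, "between baseline and each follow-up time point (0, 1 and 2 months"), and it names no covariate.

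The bullets that follow give the same 1-month comparisons to a different method. For ODI a Pearson "chi-square-test will be done to assess the significance of the difference in Oswestry low back disability score over a 1 month period", and for pain a second Pearson "chi-square will be done to assess the significance of the difference in BPI NRS pain severity score over a 1 month period". Neither test can carry a covariate.

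Section 5.1.1A defines the primary outcome as a "difference in the change in ODI score in the initial treatment visit questionnaire" and at one month, control against each active group, with no mention of adjustment. Section 2.1 names no stratification on either score. Section 2.2 sets 20 participants per group, 60 in all, and calls the study a pilot.

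**The concern.** Under randomisation a baseline difference is a chance event. Its p-value does not show whether the variable predicts outcome, and prediction is what makes a covariate useful. A screen on that p-value therefore admits the baseline score only by accident.

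Three readings are open:

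1. The screen governs. Baseline ODI or BPI is usually left out and raw changes are compared.
2. The covariance analysis is meant always to contain the baseline score, and the screen adds other variables. Nothing is lost, but this is not written.
3. The chi-square bullets govern, and no covariate enters.

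Under reading 1, a change score subtracts the whole of any chance baseline imbalance. That over-corrects when the regression slope of month 1 on baseline is below 1. What is at stake is the width of the interval for each active-versus-control difference. That matters in a pilot, whose main product is an estimate with its uncertainty. It also matters for section 1.2, which states comparative hypotheses with a 10% margin.

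**Working it through.** **Inputs from the documents.** Three groups of n = 20 (section 2.2); two-sided 0.05 (section 5.2); change from first visit to 1 month (section 5.1.1A). The sample size comes with no SD, effect or power, so there is no planned figure to reproduce.

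**Assumptions.** Baseline ODI SD s = 15; correlation r between baseline and month 1 of 0.3, 0.5 or 0.7; SD ratio k = SD(month 1)/SD(baseline) of 0.8, 1, 1.2 or 1.3; the 10% in section 1.2 read as 10 ODI points.

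**How often the screen admits the baseline score.** A single test, or a three-group F test, flags it in about 5% of trials. If any of three pairwise t-tests counts, simulation gives about 12%. Section 5.2 does not say how a t-test applies to three groups, hence the range. The score is left out in 88% to 95% of trials.

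**Variance of one active-versus-control difference.**

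- Change score: s²(1 + k² − 2rk) × 2/n
- ANCOVA: s²k²(1 − r²) × 2/n
- Ratio, ANCOVA to change score: k²(1 − r²)/(1 + k² − 2rk), which is (1 + r)/2 when k = 1

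The two variances differ by (1 − rk)² times the variance of the baseline difference. The loss is therefore zero when the slope rk equals 1.

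*Example, k = 1, r = 0.5.* Change score: 225 × (1 + 1 − 1) × 0.1 = 22.5, SE 4.74. ANCOVA: 225 × 0.75 × 0.1 = 16.9, SE 4.11. The 95% half-width is t(57 df) × SE = 2.002 × 4.74 = 9.5 points for change, and t(56 df) × SE × √(1 + 1/56) = 2.003 × 4.11 × 1.009 = 8.3 points for ANCOVA.

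**Power for 10 points.** Three-group simulation, bivariate normal data, 20,000 trials per setting, both active groups shifted. A range in the rule column covers the different ways of applying the screen.

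| k | r | Variance ratio | Half-width, change vs ANCOVA | Power, rule as written | Power, always adjusted |
|---|---|---|---|---|---|
| 0.8 | 0.3 | 0.50 | 10.2 vs 7.3 | 50–52% | 77% |
| 0.8 | 0.5 | 0.57 | 8.7 vs 6.6 | 62–64% | 84% |
| 0.8 | 0.7 | 0.63 | 6.8 vs 5.5 | 83–85% | 95% |
| 1 | 0.3 | 0.65 | 11.2 vs 9.1 | 42–43% | 57% |
| 1 | 0.5 | 0.75 | 9.5 vs 8.3 | 56% | 66% |
| 1 | 0.7 | 0.85 | 7.4 vs 6.8 | 77–78% | 82% |
| 1.2 | 0.3 | 0.76 | 12.5 vs 11.0 | 35% | 44% |
| 1.2 | 0.5 | 0.87 | 10.6 vs 10.0 | 46% | 50% |
| 1.2 | 0.7 | 0.97 | 8.3 vs 8.2 | 66% | 67% |
| 1.3 | 0.3 | 0.81 | 13.1 vs 11.9 | 32% | 38% |
| 1.3 | 0.5 | 0.91 | 11.2 vs 10.8 | 42–43% | 45% |
| 1.3 | 0.7 | 0.99 | 8.9 vs 8.9 | 60% | 60% |

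The half-widths compare a pure change score with ANCOVA; the power columns apply the screen itself. An independent repeat at k = 1 agreed to within about a point (43.5% vs 57.1%, 56.1% vs 66.3%, 77.3% vs 82.4%). At r = 0.9 with equal SDs, power is 99.6% either way.

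**Bias and type I error under the rule.** The mean estimate was 9.93 to 10.07 for a true 10. Type I error was 0.035 to 0.051 in every setting simulated.

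**Carry-forward.** Section 3.5.1 carries the last value forward. If a share p of month-1 values is carried forward with equal SDs, the analysed correlation becomes p + (1 − p)r. At an assumed p = 0.2 this is 0.44, 0.60 and 0.76, with variance ratios 0.72, 0.80 and 0.88. Power is then 33% vs 43%, 43–44% vs 51%, and 62–63% vs 67%. The mean estimate falls to about 8.0 under both analyses, which is a separate effect of carrying values forward.

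**The case against.** The strongest reply is that reading 1 is not the natural one. Section 5.2 speaks separately of outcome variables and of baseline characteristics, so the screen may be meant for age, sex, pain duration and the like. The covariance sentence is unconditional: if nothing is flagged and the screen is the only source of covariates, that analysis has no covariate. Reading 2 avoids this, and under it no precision is lost. This is a fair argument about intent. It does not supply the missing words: the sentence saying how covariates enter the model is the screen, and an analyst who follows it omits the baseline score.

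Second, the loss may be small. It nearly vanishes at r = 0.9 with equal SDs. Section 4.2.1 also lets participants see their previous pain level when rating pain, which plausibly raises r for BPI and makes r = 0.3 doubtful there. This stands, and the loss must be stated as conditional. High r is not a guarantee, however: at k = 0.8 and r = 0.9 the variance ratio is 0.64 × 0.19/0.20 = 0.61.

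Third, the tabulated half-widths slightly overstate the interval under the screen, because the screen sometimes adjusts. At k = 1 and r = 0.3 the mean half-width under the screen is 10.98 to 11.13 rather than 11.2. This is correct and immaterial.

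Fourth, section 2.2 promises no power, so none is broken, and one sentence naming the covariate would recover the precision without touching the baseline p-values. Both statements are true. The screen should still go, because otherwise the model continues to depend on chance baseline differences.

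**Conclusion.** The concern holds. The one covariate rule in the plan would omit baseline ODI and BPI in about 88% to 95% of trials, and no other text puts them in. The harm is lost precision and an undefined 1-month analysis; it is not bias or excess type I error.

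If the screen governs, the change-score interval with equal SDs is about 23%, 14% and 7% wider than ANCOVA at r = 0.3, 0.5 and 0.7, after allowing for the lost degree of freedom. Across the table, the power given up for 10 points runs from none to about 25 to 27 percentage points. These sizes rest on the assumed SDs, SD ratios, correlations and 10-point reading. If the plan intends baseline adjustment always, the loss is nil and only the wording needs repair. If the chi-square tests govern, these figures do not apply. The within-person t-tests of the follow-up study are unaffected.

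The change should be made. Confidence is medium, because the text allows more than one reading.

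**What to change.** In section 5.2, delete the baseline significance tests and the covariate rule that depends on them, and replace the covariance sentence. Suggested text:

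> Baseline data will be summarised by group without p-values. Change in ODI from the first treatment visit will be analysed by ANCOVA with group (three levels) and first-visit ODI as a fixed covariate, whatever the baseline differences. Change in BPI severity will be analysed likewise with first-visit BPI severity, using the same four-item average as the outcome. The same covariate will be used for any between-group comparison at 2 months. Each active group will be compared with control at 1 month, with a 95% CI. No covariate will be selected by significance testing.

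The BPI score has to be named because section 4.2.1 records "the average of these values as well as the pain" right now. Redirect the two chi-square bullets to this ANCOVA, stating that it is the analysis for the 1-month ODI and BPI comparisons.

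The cost is three replaced sentences and two edited bullets. No new data are needed, since both questionnaires are already given at the first visit (sections 3.2 and 4.1). Each model spends one degree of freedom. In the table the worst case is an interval about 0.5% wider (k = 1.3, r = 0.7). At a slope of exactly 1 it would be about 0.9% wider, from √(57/56) × 2.0032/2.0025 = 1.009.

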In 2018 I did a chart review of 180 cases of low back pain in which I tested those who did not have lumbar pain using the SIFFT^x. I treated them with the appropriate exercise depending on the direction of the sacroiliac rotation. From this review, I found 16 cases of pain coming from the lumbar spine (9%). Of the remaining 164 given the appropriate 2 minute exercises, 78% found pain relief of which two thirds left the office entirely pain free. At that time, I also prescribed a pelvic support belt as, generally, a malrotated pelvis is an unstable pelvis^{xi}. As soon as the pelvis becomes malrotated again, the pain recurs. As the corrective exercise and pelvic support belt are two different treatments, the current research project will study them first separately for one month, then on follow-up after they have been used together for one month.

The aim of this study is to determine whether the pain relief and improved back function is temporary or if it can be reproduced and sustained by the patient at home, as needed with these two treatments. In order to test the effectiveness of each treatment alone and when they are combined, two sub-studies will be carried out as follows:

The first study is a superiority trial with a delayed control.

Population: ambulatory people between the ages of 19 and 90 suffering from low back pain, not of lumbar spine or hip origin, for at least three months.

Intervention 1 : teaching participants how to detect pelvic malrotation using the SIFFT then prescribing a two-minute exercise to correct pelvic malrotation, depending on its direction.

Intervention 2: prescribing a pelvic support belt to stabilize the pelvis.

Control: waiting list for one month, using usual treatments such as medications, alcohol and other drugs, chiropractic and other manipulation and physical therapy.

Outcome: a clinically significant change in Brief Pain Inventory (BPI) NRS pain score or in Oswestry disability Index (ODI) for low back pain.

Time: outcomes measured at baseline and after one month of using the assigned treatment at home.

The second study is a one month follow-up of the combined treatments.

Population: all previous study participants

Intervention: teaching all participants how to detect pelvic malrotation using the SIFFT then a two-minute exercise to correct pelvic malrotation depending on its direction followed by prescription of a pelvic support belt.

Control: BPI NRS pain severity score and ODI at one month assessment

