1.2. Hypotheses

The first study aims to find out if the recently developed exercises or the use of a pelvic support belt provide more than short term pain relief in the doctor's office:

Primary Hypotheses for the first study:

1. At 1 month, there will be significantly greater improvement in the ODI for low back pain score: at least 10% greater in those who are in treatment group 1 and are immediately taught how to perform the SIFFT followed by the appropriate exercise when compared to those on the waiting list for one month prior to being treated.
2. At 1 month, there will be significantly greater improvement in the ODI for low back pain score: at least 10% greater in those who are in treatment group 2 and are immediately given the pelvic support belt when compared to those on the waiting list for one month prior to being treated.

Secondary Hypotheses for the first study:

- 1 At 1 month, there will be significantly greater improvement in the BPI NRS pain severity score in those who are in treatment group 1 and are immediately taught how to perform the SIFFT followed by the appropriate exercise when compared to those on the waiting list for one month prior to being treated.
- 2 At 1 month, there will be significantly greater improvement in the BPI NRS pain severity score in those who are in treatment group 2 and are immediately fitted with a pelvic belt when compared to those on the waiting list for one month prior to being treated.

The follow-up study aims to find out if the recently developed exercises together with the use of a pelvic support belt provided more pain relief than each individual treatment:

Primary Hypothesis for the follow-up study:

- 1 At 2 months, there will be significantly greater improvement in the ODI for low back pain score compared to their one-month score in all participants.

Secondary Hypothesis for the follow-up study:

- 1 At 2 months, there will be significantly greater improvement in the BPI NRS pain severity score compared to their one-month score in all participants.

2.0 Recruitment:

Participants making a first appointment at the clinic for back pain will be in contact with my medical office assistant, [name], and invited to participate in this study. If they would like to participate, she will send them the consent form and eligibility questionnaire. If they are eligible, she will schedule them for their first visit.

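### Section 5.2 names two competing analyses for the one-month ODI and BPI outcomes, ranks neither, leaves the chi-square categories undefined, and specifies no comparison of either treatment with the waiting list

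*Combined protocol and SAP*

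**What the plan says.** Section 1.2 states two primary hypotheses for the first study, each comparing one treatment with the waiting list at one month. The first expects "significantly greater improvement in the ODI for low back pain score: at least 10% greater in those who are in treatment group 1"; the second says the same for the belt group. Section 5.1.1A matches this with two primary outcomes, each a "difference in the change in ODI score in the initial treatment visit questionnaire and at the assessment visit one month later" in the control group set against the same change in one treated group. Section 5.1.2A repeats the pattern for BPI pain severity.

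Section 5.2 then names two analyses:

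- a model of change: "Analyses of covariates will be applied to compare the groups for magnitude of change in the 0-10 NRS pain score and Oswestry Disability Index", with this covariate rule: "Baseline characteristics will be included in the model as covariates for those variables with a significant between group difference";
- a Pearson "chi-square-test will be done to assess the significance of the difference in Oswestry low back disability score over a 1 month period" across the exercise, belt and observation groups, followed by the pain counterpart: "A second Pearson's chi-square will be done to assess the significance of the difference in BPI NRS pain severity score", across the same three groups.

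The significance level is two-sided 0.05. Neither analysis is called primary or supportive. Section 5.2 defines no ODI or BPI categories and names no pairwise test or contrast.

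**The concern.** Three faults combine.

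1. **The chi-square does not fit the outcome.** Change in ODI is numeric. A Pearson chi-square needs categories and ignores their order. Section 1.1 speaks of clinically significant change, so a responder analysis may be intended, but no cut-off for an individual appears anywhere. The 10% in section 1.2 is a difference between groups, and the text does not say whether it means ODI points or a relative change.
2. **A three-group test does not answer a pairwise question.** A significant result says only that the groups are not all alike.
3. **The covariate analysis does not fill the gap.** It names no contrasts, and it adjusts for baseline ODI only if the groups happen to differ significantly on it.

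At stake is the verdict on the primary hypotheses. With two analyses, no ranking and free choice of categories, that verdict can be settled after the data are seen.

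**Working it through.** **The plan's own figure.** Section 2.2 gives 3 × 20 = 60 participants, with no SD, effect size or power behind it. There is no calculation to reproduce.

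**Question against analysis.**

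| | Sections 1.2 and 5.1.1A | 5.2 chi-square | 5.2 covariate analysis |
|---|---|---|---|
| Comparison | exercise vs waiting list; belt vs waiting list | three groups at once | the groups; no contrast named |
| Scale | change in ODI | categories, undefined | change in ODI |
| Baseline ODI as covariate | not stated | none | only after a pretest |

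Neither analysis column delivers the two comparisons in the first.

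**Does the choice matter with 20 per group?** The following are assumptions, because the documents give none of them: the 10% is read as 10 ODI points; both treatments work; baseline mean 40; SD 10, 15 or 20 at each visit; correlation r of 0.5 or 0.7 between baseline and month 1.

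For one treatment against the waiting list:

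- SD of change = SD × √(2(1 − r)). At SD 15, r = 0.5, this is 15 × √1 = 15.0.
- Residual SD with baseline always adjusted = SD × √(1 − r²). Here 15 × √0.75 = 12.99.
- Power ≈ Φ(10 / (s × √(2/20)) − 1.96). With s = 15.0: Φ(2.108 − 1.96) = 0.56. With s = 12.99: Φ(2.434 − 1.96) = 0.68.

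For the three-group chi-square with a responder defined as improving by at least 10 points (same case):

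- Expected responders are 0.500 in each treated group and P(Z > 10/15) = 0.252 on the waiting list, so the mean proportion is 0.417.
- Noncentrality = 20 × [2(0.083)² + (0.165)²] / (0.417 × 0.583) ≈ 3.36.
- On 2 df with critical value 5.991, power ≈ 0.36.

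Simulation (4,000 trials per scenario, ODI in 2-point steps limited to 0–100) agrees. The last column is the share of trials in which the three-group F test under section 5.2's covariate rule and the responder chi-square fall on opposite sides of 0.05.

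| SD, r | Chi-sq, each score a category | Chi-sq, 10-point bands | Chi-sq, 10-point responder | Contrast, covariate only after pretest | Contrast, always adjusted | Opposite verdicts |
|---|---|---|---|---|---|---|
| 10, 0.5 | 0.08 | 0.49 | 0.67 | 0.88 | 0.94 | 0.24 |
| 10, 0.7 | 0.24 | 0.80 | 0.88 | 0.98 | 0.99 | 0.11 |
| 15, 0.5 | 0.02 | 0.14 | 0.36 | 0.55 | 0.65 | 0.28 |
| 15, 0.7 | 0.05 | 0.31 | 0.54 | 0.76 | 0.82 | 0.29 |
| 20, 0.5 | 0.01 | 0.07 | 0.21 | 0.34 | 0.43 | 0.20 |
| 20, 0.7 | 0.02 | 0.13 | 0.32 | 0.52 | 0.59 | 0.28 |

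With bands, opposite verdicts occur in 20–49% of trials; with raw scores, in 32–83%.

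**If the 10% is relative.** Ten percent of a baseline of 40 is 4 points. Always-adjusted power is then Φ(4/(17.32 × 0.3162) − 1.96) = 0.11 at SD 20, r = 0.5, and Φ(4/(7.14 × 0.3162) − 1.96) = 0.42 at SD 10, r = 0.7. The chi-square gives 0.005–0.17.

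**What a three-group result means.** If only exercise works, the responder chi-square is still significant in 22–90% of trials. If exercise improves ODI by 5 points and the belt worsens it by 5 (SD of change 12), the three-group F test is significant in about 63% of trials, but each treatment beats or trails the waiting list significantly in only about 25%.

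**Covariate rule.** Under randomization, a three-group F pretest at 0.05 admits baseline ODI in about 5% of trials. If the pretest is any of the three pairwise t-tests, the share is about 12–13%. Either way it is usually left out.

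**Two primary contrasts.** Each tested at 0.05, they carry 1 − 0.95² = 9.75% familywise error if independent, and about 9.1% with the shared control (correlation 0.5).

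**The case against.** The strongest reply is that section 2.2 justifies 20 per group only as a pilot of the design, so power and formal verdicts matter less. That softens the consequence. But section 1.1 calls the first study a superiority trial, section 1.2 predicts significant differences, and section 5.2 sets a significance level. A plan that will declare significance must say which test declares it.

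Second, sections 5.1.1A and 5.2 read together might imply pairwise contrasts from the covariate model. That reading is natural, but it is not written, and the chi-square remains beside it unranked.

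Third, the covariate sentence refers to a 0–10 NRS pain score and the chi-square to BPI NRS severity, while section 4.2.1 records both a four-item average and current pain. The two might be different variables. Section 1.1 calls the outcome the BPI NRS pain score, so overlap is the natural reading, but only for ODI is it beyond doubt.

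Fourth, analysing change already subtracts baseline. True: what is lost by omitting the covariate is precision, as the two contrast columns show.

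Fifth, treating every score as a category is the least charitable reading, and the exercise-only figure is power to detect a real difference, not an error rate. Both are fair. The responder split is the kinder case, and the discordance remains. A defined responder analysis with the tests ranked would also remove the ambiguity, but it would still need pairwise comparisons and would discard information.

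**Conclusion.** The concern holds and must be fixed. Followed as written, section 5.2 yields a three-group test on categories nobody has fixed, beside a second analysis of the same primary outcome, and neither specifies the two comparisons the hypotheses state. That conclusion rests on the text alone.

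The size rests on assumed SDs, correlations, a 10-point effect and illustrative categories. Within those ranges, grouping alone moves chi-square power from near zero to nearly 90%. Even under the responder reading, the two planned analyses disagree in roughly one trial in nine to more than one in four. No power figure is given for BPI, because the pain variable itself is not settled; the argument is the same.

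**What to change.** In section 5.2:

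- Delete both chi-square bullets.
- Name the deciding analysis: an ANCOVA of one-month ODI on group, always adjusted for baseline ODI, and separately the same for BPI severity with its own baseline. State which pain score is meant.
- Prespecify two contrasts, exercise minus waiting list and belt minus waiting list, each with a 95% confidence interval. These also serve the pilot purpose.
- If a responder analysis is wanted, make it secondary, with a stated individual cut-off.
- State whether the two primary ODI contrasts are held at 5% overall, for example by Holm.

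In section 1.2, say whether the 10% means ODI points or relative change, and whether it is a threshold for success or the expected difference.

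**Cost.** Only wording changes; no visit, measurement or sample size is affected. Always adjusting for baseline uses one degree of freedom and gains 1–10 percentage points of power over the pretest rule in the scenarios tabulated. Dropping the chi-square removes any proportion-improved result unless a secondary one is defined. Holm, if chosen, lowers pairwise power by up to about 7–8 points when both treatments work and by roughly 12 when only one does.
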